3.9.3 Vital Signs

Descriptive statistics will be presented for orthostatic systolic and diastolic blood pressure (mmHg), orthostatic pulse (beats per minute), systolic and diastolic blood pressure (mmHg), pulse (beats per minute), temperature (Celsius) and respiratory rate (breaths/min) at each visit. For each parameter, descriptive statistics on the change from baseline to each planned post-baseline visit will be presented by treatment group for the safety analysis set.

Orthostatic systolic and diastolic blood pressure will be calculated as supine measurement – standing measurement. Orthostatic pulse will be calculated as supine measurement – standing measurement.

All vital sign results will be included in a subject listing.

3.9.4 ECG

Descriptive statistics will be presented for RR interval (msec), PR interval (msec), QRS duration (msec), QTcB (msec), P wave axis (degrees) and QRS axis (degrees) for each planned visit. For each parameter, descriptive statistics on change from baseline to each post-baseline visit will be presented by treatment group for the safety analysis set.

All ECG findings will be included in a subject listing.

3.9.5 Physical Examination and Body Weight

Physical exam findings and body weight will be included in a subject listing.

3.10 Independent Data Monitoring Committee

An independent data monitoring committee (IDMC) will be established to review unblinded safety data on a regular basis and to make appropriate recommendations regarding the conduct of the trial. The study drug assignment will remain blinded to the sponsor, study team, investigators, study coordinators, pharmacists and study subjects for the course of the study. A designated unblinded statistical programming team at PROMETRIKA that is not involved with study operations will prepare the unblinded tables and listings. The selected tables and listings to be provided to IDMC members have a single asterisk (*) next to the table or listing title in Section 5 of this SAP.

4 Programming Specifications

It is suggested that computer-generated table output adhere to the following specifications.

1. Unless otherwise specified, all computer-generated tables and listings should be produced in landscape mode using SAS[®] ODS to create RTF output which can be imported by Microsoft[®] Word in table format. All output should have the following two-line header at the upper left margin:

```
Theracos Sub, LLC.  
THR-1442-C-449
```

and the following header at the upper right margin:

```
Page x of y
```

2. Each table should be identified by in a sequential numeric order, and the table designation should be centered above the title. A decimal system within the numeric numbering (i.e., x.y and x.y.z) should be used to identify tables, listings and figures with related contents. The title is centered in initial capital characters and should include the analysis set analyzed (e.g. Safety Analysis Set). The title and table designation are single-spaced, but are separated from the table by at least a double space.

```
Table No.
```

```
First Line of Title  
Second Line of Title (if needed)  
Analysis Set Analyzed
```

3. Column headings should be in proper case.
4. For variables with numeric values, include “unit” in column heading when appropriate.
5. Footnotes should be single spaced, but separated by at least a double space from the bottom line of the table. The notes are aligned vertically by the left vertical border of the table. All output should have at least the footnote about the program name and date of the program run.

```
[1] Footnote 1  
[2] Footnote 2  
[3] Footnote 3
```

```
PROGRAM: program file name
```

```
DDMMYYYY HH:MM
```

6. Unless specified otherwise, all data listings should be sorted by subject number with the study center, and by visit date within subject, where appropriate.
7. For tables that summarize categorical (discrete) data, a Missing category should be added to any parameters for which information is not available for any subject.

8. Unless otherwise specified, the estimated mean, median, first and third quartiles (Q1 and Q3, respectively) for a set of values should be printed out to one more decimal place than the raw (observed) data and rounded appropriately. Standard errors (or standard deviations) should be printed out to two additional decimal places than the raw (observed) data and rounded appropriately. For example, for age (with raw data in whole years):

n	xx
Mean (SD)	xx.x (xx.xx)
Median	xx.x
Q1, Q3	xx.x, xx.x
Min, Max	xx, xx

9. The p-values will be printed in the tables rounded appropriately to 4 decimal places and formatted as '0.xxxx'. P-values less than 0.0001 will be formatted in the tables as '<0.0001'.
10. All fractional numeric values should be printed with a zero to the left of the decimal point (e.g., 0.12, 0.3).
11. Unless otherwise specified, percentage values should be printed with one digit to the right of the decimal point (e.g., 12.8, 5.4).
12. Missing descriptive statistics due to non-estimability in tables, as well as missing data in subject listings should be represented as either a hyphen (“-“) with a corresponding footnote (“ - = unknown or not evaluated”), or as “N/A” with the footnote “N/A = not applicable” whichever is appropriate.
13. Dates printed as a result in the table, listing, or graph should be printed in SAS DATE9. format (“DDMONYYYY”: 01 JUL 2002). Missing portions of dates should be represented on subject listings as dashes (-- JUL 1999). Dates that are missing because they are not applicable for the subject should be listed as “N/A”, unless otherwise specified.

5 List of Tables, Figures and Listings

5.1 List of Tables

Table Number	Table Title	Analysis Set
Disposition, Demographics, Baseline Characteristics, Compliance and Exposure		
14.1.1*	Subject Disposition	All Enrolled Subjects
14.1.2.1*	Demographics, Screening and Disease Characteristics	Safety Analysis Set
14.1.2.2#	Demographics, Screening and Disease Characteristics	Intent-to-Treat Analysis Set
14.1.2.3#	Demographics, Screening and Disease Characteristics	Full Analysis Set
14.1.3.1	Summary of Concomitant Medications	Safety Analysis Set
14.1.3.2	Summary of Rescue Medications for Hyperglycemia	Safety Analysis Set
14.1.4	Summary of Study Treatment Duration and Compliance	Safety Analysis Set
Primary Endpoints		
14.2.1.1.1*	Summary of HbA1c (%) by Visit: Observed and Changes from Baseline	Full Analysis Set
14.2.1.1.2	Summary of HbA1c (%) by Visit: Observed and Changes from Baseline	Per Protocol Analysis Set
14.2.1.2.1	Mixed Model Repeated-Measure (MMRM) Analysis of HbA1c (%): Change from Baseline and Dose Response, Overall Model for Primary Analysis and Sensitivity Analyses	
14.2.1.2.2	Least Squares Summary Mixed Model Repeated-Measures (MMRM) Analysis of HbA1c (%): Change from Baseline, Excluding HbA1c Data Obtained After Rescue Medication (Primary Analysis)	Full Analysis Set
14.2.1.2.3	Least Squares Summary Mixed Model Repeated-Measures (MMRM) Analysis of HbA1c (%): Change from Baseline, Using Multiple Imputation (Sensitivity Analysis 1)	Full Analysis Set

Table Number	Table Title	Analysis Set
14.2.1.2.4	Least Squares Summary Mixed Model Repeated-Measures (MMRM) Analysis of HbA1c (%): Change from Baseline, Using Last Observation Carried Forward (Sensitivity Analysis 2)	Full Analysis Set
14.2.1.2.5	Least Squares Summary Mixed Model Repeated-Measures (MMRM) Analysis of HbA1c (%): Change from Baseline, HbA1c Data Obtained After Rescue Medication Considered (Sensitivity Analysis 3)	Full Analysis Set
14.2.1.2.6	Least Squares Summary Mixed Model Repeated-Measures (MMRM) Analysis of HbA1c (%): Change from Baseline, Excluding HbA1c Data Obtained After Rescue Medication Considered (Sensitivity Analysis 4)	Per Protocol Analysis Set
Secondary Endpoints		
14.2.2.1*	Summary of Fasting Plasma Glucose (mmol/L) by Visit: Observed and Change from Baseline	Full Analysis Set
14.2.2.2	Mixed Model Repeated-Measure (MMRM) Analysis of Fasting Plasma Glucose (mmol/L): Change from Baseline	Full Analysis Set
14.2.2.3	Least Squares Summary Mixed Model Repeated-Measure (MMRM) Analysis of Fasting Plasma Glucose (mmol/L): Change from Baseline	Full Analysis Set
14.2.3.1	Summary of Sitting Systolic Blood Pressure (mmHg) by Visit: Observed and Change from Baseline	Full Analysis Set
14.2.3.2	Mixed Model Repeated-Measure (MMRM) Analysis of Sitting Systolic Blood Pressure (mmHg): Change from Baseline	Full Analysis Set

Table Number	Table Title	Analysis Set
14.2.3.3	Least Squares Summary Mixed Model Repeated-Measure (MMRM) Analysis of Sitting Systolic Blood Pressure (mmHg): Change from Baseline	Full Analysis Set
14.2.4.1	Summary of Sitting Diastolic Blood Pressure (mmHg) by Visit: Observed and Change from Baseline	Full Analysis Set
14.2.4.2	Mixed Model Repeated-Measure (MMRM) Analysis of Sitting Diastolic Blood Pressure (mmHg): Change from Baseline	Full Analysis Set
14.2.4.3	Least Squares Summary Mixed Model Repeated-Measure (MMRM) Analysis of Sitting Diastolic Blood Pressure (mmHg): Change from Baseline	Full Analysis Set
14.2.5.1	Summary of Body Weight (kg) by Visit: Observed and Change from Baseline	Full Analysis Set
14.2.5.2	Mixed Model Repeated-Measure (MMRM) Analysis of Body Weight (kg): Change from Baseline	Full Analysis Set
14.2.5.3	Least Squares Summary Mixed Model Repeated-Measure (MMRM) Analysis of Weight (kg): Change from Baseline	Full Analysis Set
14.2.6	Logistic Regression Analysis of Subject Achieving Post-baseline HbA1c <7%, Excluding HbA1c Data Obtained After Rescue Medication	Full Analysis Set
Safety Endpoints – Adverse Events		
14.3.1.1	Overall Summary of Treatment Emergent Adverse Events	Safety Analysis Set
14.3.1.2	Summary of Treatment Emergent Adverse Events by MedDRA System Organ Class and Preferred Term	Safety Analysis Set
14.3.1.3	Summary of Treatment Emergent Adverse Events by MedDRA System Organ Class, Preferred Term and Maximum Severity	Safety Analysis Set

Table Number	Table Title	Analysis Set
14.3.1.4	Summary of Related Treatment Emergent Adverse Events by MedDRA System Organ Class and Preferred Term	Safety Analysis Set
14.3.2	Summary of Treatment Emergent Adverse Events of Special Interest by MedDRA System Organ Class and Preferred Term	Safety Analysis Set
14.3.3	Summary of Hypoglycemic Events by Category and Logistic Regression Analysis of Subjects with a Post-baseline Hypoglycemic Event	Safety Analysis Set
Safety Endpoints – Clinical Laboratory		
14.3.4.1.1*	Summary of Hematology: Observed and Change from Baseline by Visit	Safety Analysis Set
14.3.4.1.2*	Shift from Baseline in Hematology Laboratory Parameters	Safety Analysis Set
14.3.4.2.1*	Summary of Serum Chemistry, Electrolytes, Glycemic Control and Serum Lipid Laboratory Parameters: Observed and Change from Baseline by Visit	Safety Analysis Set
14.3.4.2.2*	Shift from Baseline in Serum Chemistry, Electrolytes, Glycemic Control and Serum Lipid Laboratory Parameters	Safety Analysis Set
Safety Endpoints – Vital Signs and 12-Lead ECG		
14.3.5*	Summary of Vital Signs: Observed and Change from Baseline by Visit	Safety Analysis Set
14.3.6	Summary of 12-Lead Electrocardiogram: Observed and Change from Baseline by Visit	Safety Analysis Set

* Table is to be provided to the IDMC. For Table 14.1.2.1, disease characteristics will not be included. For Table 14.3.4, only the following lab parameters will be included: ALT, AST, Creatinine, Bicarbonate and Hemoglobin. For Table 14.3.5, only orthostatic systolic and diastolic blood pressure will be included.

Only performed if intent-to-treat analysis set and/or full analysis set are different from the safety analysis set.

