9.7 Interim Analysis

There will be no interim analysis. The final analysis will be performed after all subjects have completed the follow up assessments and all subject data have been cleaned and locked in the study database.

An independent Data and Safety Monitoring Board (DSMB) will monitor the safety of the subjects in this study. The objectives of the DSMB are to assess drug safety and to allow for protocol modification or early stopping due to safety concerns.

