3.8.1 Primary Efficacy Endpoint(s)

The primary endpoint is HbA1c change from baseline through 12 weeks, and the primary analysis is based on the available data and data obtained after rescue will be excluded and considered missing. Mixed model repeated measures (MMRM) analysis of covariance model (ANCOVA) with baseline HbA1c as a covariate will be fit to the available data, incorporating all visits at which HbA1c was measured for each subject including scheduled visits at Weeks 2, 6, and 12 as well as unscheduled visits for measurements of HbA1c. Treatment (placebo, 5 mg, 10 mg, 20 mg), study center, prior anti-diabetic treatment status, study visit and treatment-by-visit interaction will be applied as fixed effects and subject as a random effect.

A normal distribution will be assumed for the built-in probability distribution. Model assumption will be checked. An unstructured (UN) within-subject covariance structure will also be assumed. The Kenward-Roger approximation will be used to estimate the denominator degrees of freedom.

Sample SAS code for this analysis is as follows:

```
proc mixed data=temp method=reml covtest;  
  class subject visit treat prior center;  
  model change = visit treat prior center baseline visit*treat /  
  solution ddfm=KENWARDROGER;  
  repeated visit / subject=subject type=un;  
  lsmeans visit*treat / diff=all cl alpha=0.05;  
run;
```

In the case that this covariance matrix is not an appropriate estimate, other covariance structures (e.g., compound symmetry) will be considered and ultimately determined through graphical tools (i.e., plot of changes in covariance and correlation among residuals on the same subject over lag between times of observation) and information criteria [e.g., Akaike's Information Criteria (AIC)].

Descriptive statistics will be presented for the observed measurements as well as for change from baseline by treatment group and visit overall (all subjects) and by country.

Least squares (LS) means and the corresponding standard errors (SE) of the change from baseline over time will be presented by treatment. In addition, the time profile of these LS mean and SE values will be presented graphically.

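### The safety monitoring committee is sent by-arm HbA1c and glucose summaries but no by-arm summary of adverse events, special-interest events or hypoglycemia, and no bilirubin values

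*SAP*

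**What the plan says.** SAP 3.10 creates a committee that "will be established to review unblinded safety data on a regular basis" and may make recommendations on trial conduct. The same section says what it is sent: "The selected tables and listings to be provided to IDMC members have a single asterisk (*) next to the table or listing title". A designated unblinded programming team prepares this material.

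Protocol 9.7 plans no interim analysis and describes the board's role: "The objectives of the DSMB are to assess drug safety and to allow for protocol modification or early stopping due to safety concerns". Protocol 3.2.3 and 10.8 leave the board's review activity and risk-benefit assessments to a charter, which is not among the documents.

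Among the tables in SAP 5.1, the HbA1c summary (14.2.1.1.1) and the fasting plasma glucose summary (14.2.2.1) are marked. SAP 3.8.1 says the HbA1c descriptive statistics cover "change from baseline by treatment group and visit overall (all subjects) and by country". The four laboratory tables and the vital signs table are also marked, with restrictions in the footnote. Vital signs are cut to orthostatic blood pressure, and for the laboratory tables "only the following lab parameters will be included: ALT, AST, Creatinine, Bicarbonate and Hemoglobin".

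Two tables without an asterisk are 14.3.1.1, "Overall Summary of Treatment Emergent Adverse Events", and 14.3.2, "Summary of Treatment Emergent Adverse Events of Special Interest by MedDRA System Organ Class and Preferred Term". In SAP 5.3 the adverse-event listing (16.2.7.1) is marked. The listings of serious adverse events (16.2.7.2), clinically significant laboratory abnormalities (16.2.8.4) and hypoglycemic events (16.2.16) are not.

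**The concern.** The reason for showing unblinded data to a committee is to let it compare arms. Here it gets arm-level summaries of two efficacy measures, but no arm-level count of any adverse event. Genital infection, urinary tract infection, volume depletion, hypoglycemia and serious events are all harms on which the arms could differ. To see a difference, members would have to count preferred terms in a listing and find the denominators elsewhere. A moderate imbalance is easy to miss that way, and two members may count differently.

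The liver data raise a narrower question. Protocol 6.10.8 pairs raised ALT or AST with raised total bilirubin in one of its hepatotoxicity criteria, yet the committee's laboratory output has the enzymes without bilirubin.

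**Working it through.** The plan states no figure on this point. The check is a count of asterisks, followed by a comparison of sections.

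**Tables (SAP 5.1)**

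| Group | Tables | Marked | Which |
|---|---|---|---|
| Disposition, baseline, medication, exposure | 7 | 2 | 14.1.1, 14.1.2.1 |
| Primary efficacy | 8 | 1 | 14.2.1.1.1 (HbA1c) |
| Secondary efficacy | 13 | 1 | 14.2.2.1 (FPG) |
| Adverse events, special interest, hypoglycemia | 6 | 0 | none |
| Laboratory | 4 | 4 | 14.3.4.1.1, 14.3.4.1.2, 14.3.4.2.1, 14.3.4.2.2 (five analytes only) |
| Vital signs and ECG | 2 | 1 | 14.3.5 (orthostatic blood pressure only) |

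Total: 7 + 8 + 13 + 6 + 4 + 2 = 40. Marked: 2 + 1 + 1 + 0 + 4 + 1 = 9. The six unmarked safety tables are 14.3.1.1 to 14.3.1.4, 14.3.2 and 14.3.3.

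**Listings (SAP 5.3)**

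Four of 28 are marked: 16.2.1, 16.2.4, 16.2.5.2 and 16.2.7.1. Only the last carries adverse events. Its footnote describes a split into run-in failures and randomized subjects, and mentions no counts by arm.

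**What Listing 16.2.7.1 should contain**

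- Serious events: Listing 16.2.7.2 is by its title a subset of 16.2.7.1.
- Hypoglycemia: SAP 3.9.1.7 enters four of the five categories as adverse events; only relative hypoglycemia is left out.
- Liver: protocol 6.10.8 enters hepatotoxicity as an adverse event, and protocol 6.10 makes any AST, ALT or bilirubin rise above 3 x ULN a laboratory adverse event.

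**Special-interest categories**

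SAP 3.9.1.6 lists 12. The marked tables bear indirectly on five: hepatotoxicity (ALT, AST), renal failure (creatinine), acid-base disorders (bicarbonate), and hypotension and diuretic effects (orthostatic blood pressure). That leaves 12 - 5 = 7 for which no marked table is directed at the events: genital mycotic infection, urinary tract infection, MACE, hypoglycemia, falls and fractures, malignancy and hypersensitivity.

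Members would also have to sort terms into categories without a list. Protocol 9.6.2 says the terms will be in the SAP, but SAP 3.9.1.6 leaves them to a blinded review of the data.

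**Bilirubin**

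Total bilirubin is in the chemistry panel (protocol Table 1), and chemistry is drawn at S1, S5, V2, V4 and V5 (protocol Appendix 2). The footnote keeps it out of the marked tables. The chemistry listing (16.2.8.2) and Listing 16.2.8.4 are unmarked. Bilirubin values are therefore in no output that the SAP sends to the committee.

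Adding bilirubin to the laboratory tables would not be enough. SAP 3.9.2 describes those tables as descriptive changes and low/normal/high shifts, one parameter at a time. They cannot show two abnormalities in the same subject or a multiple of the ULN. Only subject-level output can.

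**The case against.** The strongest reply is that what is missing is aggregation, not information. The committee holds the full adverse-event listing, prepared by an unblinded team. It also has by-arm laboratory and blood pressure tables that bear on five special-interest categories. That is correct, and it limits the point. A reader might infer that the committee receives no adverse-event data or cannot see harms; Listing 16.2.7.1 rules that out. A reader might likewise infer that liver injury would go unseen, but qualifying cases should be in that listing.

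The charter may call for more outputs, and protocol 5.5 lets treatment information go to the board to evaluate a rise in serious suspected adverse reactions. This stands as a caveat. But if the charter asks for more, the SAP list is incomplete; if it does not, the gap is real. The SAP text needs attention either way.

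The HbA1c and glucose tables can be defended, since benefit-risk assessment needs them and they show loss of glycemic control. Supplying them is not the fault.

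It is also tempting to call the committee the trial's only route to early stopping. Protocol 6.12 lets the sponsor or investigator terminate the study, so that reading fails.

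Finally, Table 14.3.3 includes a logistic regression with study center as a predictor. Center pooling is settled only at blinded review before lock (SAP 3.1.8), and protocol 9.7 plans no interim analysis. Marking that table unchanged would add an unneeded test. This objection stands, and the fix allows for it.

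**Conclusion.** The point holds as a gap in presentation. None of the six by-arm adverse-event, special-interest and hypoglycemia tables goes to the committee, while two efficacy summaries do. Adverse events arrive only as a subject-level listing, so by-arm comparison depends on hand tallying. Bilirubin values are in no marked output, although cases that meet the protocol's definition should be reported as adverse events.

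This rests on three assumptions: that the SAP's IDMC and the protocol's DSMB are the same body, that the asterisks define the routine package, and that the unseen charter does not already require these summaries. The documents do not support saying that harms are hidden from the committee or that it cannot do its work. They support saying that by-arm comparison is made harder than it need be, when suitable tables are already specified. The change is worth making; no efficacy result depends on it.

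**What to change.** - Add the asterisk to Tables 14.3.1.1, 14.3.1.2 and 14.3.2, and to the category counts of 14.3.3 without its logistic regression.
- Add it to Listings 16.2.7.2 and 16.2.16.
- Fix the special-interest preferred terms before the first committee review. This also brings the SAP into line with protocol 9.6.2.
- Add total bilirubin to the laboratory footnote in SAP 5.1. In addition, either mark Listing 16.2.8.4 or supply a subject-level listing of ALT, AST and bilirubin, so that concurrent elevations can be seen. The dedicated listing is the surer choice, because 16.2.8.4 holds only abnormalities judged clinically significant.
- Check the resulting list against the committee charter and make the two agree.

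The cost is SAP wording, a somewhat larger package for the unblinded team to prepare, and an earlier special-interest term list. Sample size and alpha do not change. Sponsor blinding is unaffected, because the team that prepares the package is already separate from study operations.

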9.6.2 Adverse Events of Special Interest

Adverse events of special interest include the following categories:

- Genital mycotic infections
- Urinary tract infections including urosepsis and pyelonephritis
- Diuretic effects including hypovolemia
- Hypotension episodes
- Hepatotoxicity
- MACE
- Hypoglycemia
- Falls and fractures
- Malignancies
- Hypersensitivity reactions
- Acid-base disorders
- Renal failure events

AEs of special interest will be defined programmatically based on MedDRA system organ class and preferred term which will be predefined by a blinded medical reviewer and will be specified in the Statistical Analysis Plan.

Event terms, signs, and symptoms will be documented in the listings. The number and percentage of subjects who have experienced TEAEs of special interest will be summarized for each treatment group by type of AE.

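### The only blood-pressure measurement the SAP lists for the IDMC is the supine-minus-standing difference, so a fall common to both positions, or a rise in pulse, is not visible in its vital-sign data

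*SAP*

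**What the plan says.** SAP 3.10 sets up regular IDMC review of unblinded safety data and states how its outputs are chosen: "The selected tables and listings to be provided to IDMC members have a single asterisk (*) next to the table or listing title".

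In SAP 5.1 the vital-sign table, 14.3.5 ("Summary of Vital Signs: Observed and Change from Baseline by Visit"), carries the asterisk. The footnote then limits what the IDMC sees of it: "For Table 14.3.5, only orthostatic systolic and diastolic blood pressure will be included". SAP 3.9.3 gives the definition: "Orthostatic systolic and diastolic blood pressure will be calculated as supine measurement – standing measurement". The same section lists systolic and diastolic pressure, pulse and orthostatic pulse as separate parameters of the full table.

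Table 14.2.3.1 ("Summary of Sitting Systolic Blood Pressure (mmHg) by Visit: Observed and Change from Baseline") has no asterisk. Nor do the other sitting blood-pressure tables (14.2.3.2 to 14.2.4.3), the two blood-pressure figures in SAP 5.2, or Listing 16.2.10 (vital signs) in SAP 5.3.

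Protocol 9.6.2 names hypotension episodes and "Diuretic effects including hypovolemia" as events of special interest. Protocol 9.7 describes the board's task: "The objectives of the DSMB are to assess drug safety and to allow for protocol modification or early stopping due to safety concerns". The protocol calls this body the DSMB and SAP 3.10 calls it the IDMC. I take them to be the same body.

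**The concern.** A difference between two positions carries no information about the level in either. The trial expects blood pressure to matter: its effect on systolic and diastolic pressure is a secondary objective (Protocol 2.2), and hypotension and volume-related effects are on the special-interest list. Yet the committee that may prompt modification or early stopping for safety is listed to receive only a contrast from which any shared fall has been removed. It could not use its vital-sign table to compare pressure or pulse levels between the three doses and placebo. The missing values are already being collected: Protocol 6.4.1 has pressure and pulse taken sitting, supine and standing and entered in the CRF.

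**Working it through.** The plan gives no figure on this point, so there is nothing to reproduce. The check has two parts.

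**1. Which blood-pressure or pulse outputs go to the IDMC (asterisks in SAP 5.1 to 5.3)**

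| Output | Asterisk | Shows level? |
|---|---|---|
| Table 14.3.5, vital signs | Yes, restricted to orthostatic pressure | No |
| Tables 14.2.3.1 to 14.2.4.3, sitting pressure | No | Yes |
| Figures 14.2.2.2 and 14.2.2.3, sitting pressure | No | Yes |
| Listing 16.2.10, vital signs | No | Yes |

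Pulse appears only in Table 14.3.5 and Listing 16.2.10. The footnote removes it from the first, and the second is not sent.

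**2. What the difference can show**

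Let O = supine − standing (SAP 3.9.3). Then

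change in O = (change in supine) − (change in standing).

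If both positions fall by the same amount c, the change in O is (−c) − (−c) = 0 for every c. The documents state no expected blood-pressure change, so all values below are assumptions chosen to show the range.

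| Baseline supine/standing (mmHg) | Change supine | Change standing | O before | O after | Reported change |
|---|---|---|---|---|---|
| 130/128 | −25 | −25 | 2 | 105 − 103 = 2 | 0 |
| 130/125 | −5 | −5 | 5 | 125 − 120 = 5 | 0 |
| 130/125 | −30 | −30 | 5 | 100 − 95 = 5 | 0 |
| 130/125 | −20 | −30 | 5 | 110 − 95 = 15 | +10 |
| 130/125 | −5 | −20 | 5 | 125 − 105 = 20 | +15 |
| 130/125 | 0 | −20 | 5 | 130 − 105 = 25 | +20 |
| 130/125 | −10 | −8 | 5 | 120 − 117 = 3 | −2 |

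The first three rows are uniform falls of 5 to 30 mmHg, and all report 0. In the next three, standing pressure falls more than supine and the table does respond, but only to the excess: with −20 and −30 it reports +10 and hides the shared 20. In the last row both pressures fall, yet the table shows a smaller postural drop.

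The same holds for group means, because the mean of O is mean supine minus mean standing. The observed values in the table do not restore the level, since they are differences too.

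**The case against.** A reader might infer that hypotension or volume depletion in general would appear to the IDMC as no change. The documents do not support that, for three reasons.

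- Only the shared part of a fall cancels. Protocol 6.4.1 takes supine and standing readings in order to assess orthostatic effects, and a larger fall on standing raises the difference. The retained variable is the right one for a postural fall and should stay.
- The IDMC has other sources. Listing 16.2.7.1 (adverse events) is asterisked, so reported hypotension or hypovolemia reaches it by subject. It also receives creatinine, bicarbonate and hemoglobin, which bear indirectly on volume status.
- Protocol 3.2.3 and 10.8 leave the board's review activity to a charter that was not supplied. It may provide more data, and nothing in the SAP bars the committee from asking for the full table.

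These points narrow the concern but do not remove it. The adverse-event route depends on a measured fall being reported as an event. Protocol 6.5 and 6.10 state explicitly that a clinically significant ECG or laboratory change is an adverse event; Protocol 6.4 has no matching rule for vital signs. The general definition in Protocol 6.10 does cover unfavorable signs, and Protocol 3.2.3 asks for special-interest signs and symptoms to be documented, but whether an asymptomatic reading qualifies is left to judgment. Events are elicited by an open question (Protocol 6.10.1). Symptoms of urinary and genital infection are asked about specifically (6.10.6, 6.10.7), and no such query is set out for hypotension. The summary of special-interest events, Table 14.3.2, is not asterisked either.

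Keeping efficacy data from the committee would not explain the omission, because it already receives HbA1c (Table 14.2.1.1.1) and fasting glucose (Table 14.2.2.1) by visit.

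It is also fair to say that no study analysis is affected. The full vital-sign table and the sitting-pressure tables remain planned for the study report.

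**Conclusion.** The point holds in a limited form. Under the SAP's own list, the vital-sign data sent to the IDMC contain no blood-pressure level and no pulse. A uniform fall of any size gives a reported change of exactly 0, and when the falls are unequal only their difference is shown. That result is algebra and does not depend on the values assumed above. How likely or how large such a fall would be cannot be judged from the documents, because they give no expected blood-pressure effect.

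The gap lies in the vital-sign measurements and not in everything the IDMC sees: it matters for a measured fall, or a rise in pulse, that is not reported as an adverse event. The conclusion assumes that the asterisks describe the whole package and that the charter adds no vital-sign data. It is worth correcting because the trial names hypotension as an event of special interest and the remedy is very cheap.

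**What to change.** Amend the Table 14.3.5 sentence in the SAP 5.1 footnote so that the IDMC version contains systolic and diastolic blood-pressure levels and pulse, observed and as change from baseline, together with the orthostatic differences. Name the position or positions to be shown, since SAP 3.9.3 lists these parameters without stating one. Deleting the restriction, so that the full table is sent, would have the same effect.

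A smaller alternative is to asterisk Tables 14.2.3.1 and 14.2.4.1. That supplies sitting pressure levels but no pulse. It also uses the full analysis set, which requires a post-randomization HbA1c value, and not the safety analysis set.

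If the charter already provides these data, a cross-reference in SAP 3.10 is enough.

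The cost is one footnote and a slightly longer IDMC package. The data are already collected and the full table already specified. Neither the type I error rate nor the primary analysis is affected.
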